**Unanticipated Problems, Adverse Events, and Protocol Deviations:**

**NIH IRB and CD reporting**

**Definitions:** The PI or designee will refer to definitions of reportable events per Policy 801.

**Expedited reporting:** Events requiring expedited reporting will be submitted to the IRB per Policy 801 “Reporting Research Events.

**Reports to the IRB at the time of continuing review:** The PI or designee will refer to HRPP Policy 801 “Reporting research events” to determine IRB reporting requirements. In addition, an independent medical monitor will monitor all adverse events. (See section on Data and Safety Monitoring.)

### **Analysis**

Our statistical model for specific Aims 1-3 will compare variables of interest between and within the AET+ and CON groups at baseline and post-intervention with a 2-way mixed model analysis of variance (2-way ANOVA). Should there be baseline differences in the specific variable of interest or in demographic characteristics, we will use an analysis of covariance (ANCOVA) to control for the group equality, but the study will be powered under the assumption that no informative covariates are identified and using 6MWT as the primary outcome.

In Specific Aim 1 we will test the hypothesis that AET+ will improve scores on measures of PWC. The dependent variables for this Aim include total distance covered and fatigability index on the 6MWT, and peak WR achieved on the tCPET. 6MWT distance is the primary outcome variable for this RCT and thus our project is powered on the sample size estimated to achieve a significant outcome on this variable (See Sample Size below).

In Specific Aim 2, we will test the hypothesis that after AET+, significant increases in AT-time and muscle oxygenation will be observed over CON. The main dependent variables for this aim are AT-time and measures of muscle oxygenation which include [Tot-Hb], [O2-Hb], [H-Hb], and StO2 measured during tCPET and muscle arterial occlusion cuff tests. Additional dependent variables will include Qt and its components HR and SV measured during tCPETs.

In Specific Aim 3 we will test the hypothesis that patients will report decreased fatigue severity, increased physical activity, and improvements in other HRQoL. The dependent variable score for fatigue severity will be the Fatigue Severity Scale score. The dependent variable score for physical activity will be the Human Activity Profile maximum and average scale scores, and the scores for HRQoL will be composite and domain scores for the SGRQ-I, SF-36v2, and K-BILD.

In the crossover sub-study, we will determine if AET+ induces significant improvements in the variables of interest in the CON group. For this analysis we will use repeated measures ANOVA’s to determine differences in the variables of interest among baseline, 10-week post control, and 2-week post crossover AET data points. Dependent variables will be those in each of the specific aims characterized above.

In Specific Aim 4, relationships between the post-study physiological variables and health outcome variables will be determined using Pearson product moment correlations and appropriate nonparametric procedures.

In all of the analyses, statistical significance will be interpreted as the probability of making a type 1 error equal to or less than 5% ( $p \leq 0.05$ ).

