of the six minutes the subject will be asked to stop and immediate post-exercise pulse rate and oxygen saturation will be recorded. The subject will then be asked to rest in a seated position and pulse rate will be recorded during each minute of recovery for a total of ten minutes to evaluate the subject's ability to recover from intense activity. Supplemental oxygen will be provided for those patients that require supplemental oxygen while exercising and/or resting. Those subjects requiring supplemental oxygen will be provided supplemental oxygen with the same delivery device and flow pre/post intervention to maintain consistency. The target endpoint for this test is the completion of the six minutes of walking however symptomatic endpoints for stopping the tests will be those recommended by the American College of Sports Medicine. Additionally should any subject's oxygen saturation desaturate to  $\leq 80\%$  the patient will be required to stop walking at this point with or without the presence of symptoms of severe dyspnea. The patient will rest, while the timer continues to run, until oxygen saturation returns to baseline values or above 90% at which point the patient will resume walking again. The main outcome variable for this project is the change in 6MWT distance from before to after the AET+ and control regimens. The performance fatigability index will be calculated as the ratio of the 1.5-minute walking speed to the walking speed calculated over the entire 6 minutes of the test divided by the total distance covered on the test. The perceived fatigability index will be calculated by having the subject rating their feeling of tiredness prior to the 6MWT and measuring the change in tiredness after the 6MWT. The change in tiredness divided by the total distance walked will be computed as the perceived fatigability index.

Blood glucose of diabetic patients will be monitored before and after testing, and as clinical necessary. Testing will be performed by qualified staff using NIH glucometer or patient's own glucometer. In order to use patient's own glucometer, it must first be validated for accuracy through the NIH Department of Laboratory Medicine.

Fatigue Scale Items (Use before Walking Test)	Score	Fatigability Scale Items (Use After Walking Test)
Extremely Tired	7	Extremely More Tired
Somewhat Tired	6	Somewhat More Tired
A Little Tired	5	A Little More Tired
Neither Tired Nor Energetic	4	Neither More Tired Nor More Energetic

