## Sample Size:

The broad objective of the proposed work is based on identifying effects of exercise on, and relationships among, measures of physical work capacity, fatigability, oxidative metabolism, tissue oxygen extraction, and clinical outcomes. The proposed study builds upon the PI's preliminary study of the feasibility and safety of exercise treatment for patients with ILD in which the 6MWT was the primary improvement metric. Many of the hypotheses proposed under this objective require measurement of variables not included in prior studies of the ILD population. Conversely, there are established standards for clinically relevant changes in the 6MWT and multiple studies of ILD patients with which to inform our sample size decisions and 6MWT is the primary outcome variable for the proposed study. For these reasons we will power the study on 6MWT. Specifically, changes in 6MWT distance between baseline and the second testing period are compared for ILD patients randomized to the AET+ and CON arms using a 2-way mixed model ANOVA. From this, we have determined our goal is to recruit 60 patients with ILD (30 into each group) over the duration of this study, with details below.

The prior information, assumptions, and calculation for the power analysis that was conducted are as follows. An increase in 6MWT distance of 54 to 80 m exceeds the MCID in patients with ILD. Previous studies by Holland et al. and Nishiyami et al. on exercise interventions in ILD patients have observed in post-hoc independent t-test an effect size between experimental and control groups of 0.65 and 0.86, respectively, with an increase in 6MWT distance of 31 to 42 m in the experimental group. Effect sizes in this range are associated with high-moderate to large differences.

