In order to translate the existing literature's results into predictions of effect size of the 2-way mixed model ANOVA we will use as our primary statistical test, simulations were run in STATA. Simulations were drawn from normal distributions for each of control and exercise groups with equal mean and variance chosen as the average of the mean and variance observed in the control and exercise groups in Holland et al. Specifically, both groups were assumed to have mean 6MWT of 385 m and standard deviation 127 m at baseline in the simulation. The control group was assumed in all samples to show no change between baseline and retest, while different simulations were run for improvement in the exercise group of 25, 30, 35, and 40 m between baseline and retest. We did not simulate differences smaller than 25 m as this is below the MCID. At each level of improvement from treatment we simulated 3000 samples from both control and exercise groups at test-retest correlations of 0.25, 0.30, 0.35, and 0.40.

It was not possible to determine from the previously published ILD literature what level of correlation to expect between test and retest. The preliminary study performed by NIH observed a correlation of 0.840 between pre and post-treatment 6MW distances. We expect a weaker correlation between patients assigned to the CON arm of the proposed study, however, due to the conflicting effects of education and possible decline from the progression of ILD. Additionally, informal study of the plots of pre-post test change in Elia et al. also suggest the range of correlation simulated is conservative. As we are powering on only one of the multiple study aims due to the limitations of prior data and the hierarchy of study goals, we feel it prudent to risk overpowering on this outcome by using overly conservative estimates as it may ensure proper power for the other study aims.

The ranges of improvement in the treatment group and test-retest correlations considered give rise to 16 simulated data sets of 6000 observations each. Each data set was then tested with a 2-way mixed model ANOVA and the effect size recorded. Simulated effect sizes increased across the

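### Baseline adjustment of 6MWT distance hangs on an undefined baseline difference; naming an always-adjusted ANCOVA as primary fixes the model in advance and costs almost nothing

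*Combined protocol and SAP*

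**What the plan says.** The Analysis section applies a 2-way mixed ANOVA to Aims 1–3, between and within arms, at baseline and post-intervention. It then adds: "Should there be baseline differences in the specific variable of interest or in demographic characteristics, we will use an analysis of covariance (ANCOVA". The same sentence says that "the study will be powered under the assumption that no informative covariates are identified". It does not say how a baseline difference is to be judged or which demographics count.

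The Sample Size section gives the model without that contingency. Changes in distance are "compared for ILD patients randomized to the AET+ and CON arms using a 2-way mixed model ANOVA", and the simulations are run for the "2-way mixed model ANOVA we will use as our primary statistical test". The six-minute walk text under Research Tests defines the outcome in the same terms: "The main outcome variable for this project is the change in 6MWT distance from before to after the AET+ and control regimens".

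Under Study Design and Methods and under Randomization, baseline testing is completed before allocation. The covariate therefore exists for every randomised subject.

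**The concern.** Under randomisation a baseline difference is chance. Its size does not show whether adjustment is worthwhile; that depends on how strongly baseline predicts follow-up. A rule driven by the observed imbalance therefore looks at the wrong quantity. Because it is undefined, two analysts could run different primary models and both be following the plan.

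Two things are at stake. One is the error rate, if the model can be settled after the results are visible. The other is precision. With two time points the group-by-time test is a t-test on change scores, which fixes the baseline slope at 1. ANCOVA estimates that slope.

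**Working it through.** **Inputs.** From Sample Size: 30 per arm; "both groups were assumed to have mean 6MWT of 385 m and standard deviation 127 m at baseline in the simulation"; planning correlations 0.25–0.40; and "The preliminary study performed by NIH observed a correlation of 0.840 between pre and post-treatment 6MW distances". The hypothesised difference of 30 m is from Specific Aim 1, and the 5% significance level from Analysis. The plan gives no follow-up SD. Let k be follow-up SD divided by baseline SD: k = 1 is my assumption, with range 0.9–1.2.

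**The plan's own figure.** For the group-by-time F test with f = 0.25 and r = 0.40, the noncentrality is f² × N × 2/(1 − r). N = 66 gives 13.75 and power 0.955; N = 64 gives 0.949; N = 40 gives 0.803. The stated 33 per group for power 0.95, and 0.803 with 20 per group, both reproduce. The power basis is thus the change-score test.

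**Variance, change score over ANCOVA.** The large-sample ratio is (1 + k² − 2rk) / [(1 − r²)k²] = 1 + (1 − rk)² / [k²(1 − r²)], which is never below 1. At 30 per arm, estimating the slope multiplies the ANCOVA variance by 1 + 1/56 = 1.0179. The ratio is divided by that and cannot fall below 0.982. With k = 1 the large-sample ratio is 2/(1 + r), or 1.60, 1.43 and 1.09 before the division.

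| k | r = 0.25 | r = 0.40 | r = 0.84 |
|---|---|---|---|
| 0.9 | 1.76 | 1.57 | 1.23 |
| 1.0 | 1.57 | 1.40 | 1.07 |
| 1.1 | 1.44 | 1.29 | 1.00 |
| 1.2 | 1.34 | 1.20 | 0.98 |

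At k = 1, standard errors (change score, ANCOVA) are 40.2 and 32.0 m, 35.9 and 30.3 m, 18.5 and 17.9 m. A change-score analysis would need 60 × ratio = 94, 84 or 64 subjects to match ANCOVA with 60.

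**Unequal correlations.** Sample Size expects a weaker correlation in CON than in the pilot. Take CON r = 0.40, AET+ r = 0.84 and k = 1. The common slope is 0.62. The change-score variances sum to 1.20 + 0.32 = 1.52 and the ANCOVA variances to 0.8884 + 0.3428 = 1.2312, in units of SD². The ratio is 1.52/1.2312/1.0179 = 1.21. Over k = 0.9 to 1.2 it runs from about 1.37 to 1.05.

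**Simulation.** 100,000 trials per setting, k = 1, trigger on baseline 6MWT distance only; the demographic route is not modelled. Each cell gives r = 0.25 / 0.40 / 0.84.

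| Rule | Type I error | Power for 30 m |
|---|---|---|
| Change score always | 5% / 5% / 5% | 11% / 13% / 36% |
| ANCOVA if baseline p≤0.05 | 3.9% / 4.2% / 4.8% | 10% / 12% / 36% |
| ANCOVA if baseline p≤0.20 | 3.1% / 3.5% / 4.6% | 10% / 12% / 36% |
| ANCOVA always | 5% / 5% / 5% | 15% / 16% / 38% |
| Smaller p-value taken | 7.9% / 7.5% / 6.1% | not a valid test |

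The last row is from a run of 40,000 trials; repeat runs stayed between 6% and 8%. With unequal correlations, power is 17% for the p≤0.05 trigger and 21% for ANCOVA always.

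**The case against.** **The gain is small where there are data.** The plan itself calls its 0.25–0.40 range conservative, and the only observed correlation is 0.84, where the ratio is 1.07. The cited trials may point higher still. The plan reports "an effect size between experimental and control groups of 0.65 and 0.86, respectively, with an increase in 6MWT distance of 31 to 42 m". If those effect sizes are on change, CON did not change, and the figures pair in order, the SD of change is 31/0.65 = 47.7 m or 42/0.86 = 48.8 m. Then r = 1 − 47.7²/(2 × 127²) = 0.93 and the ratio is 1.02. This stands, and precision should not be oversold. But the 0.84 comes from treated patients only, the plan expects less in CON, and the most that adjustment can cost is about 1.8% of variance.

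**Deleting the ANCOVA clause would also close the trigger.** True. It would give a valid, pre-specified test but forgo the precision gain. ANCOVA also does not answer the planned within-group comparisons, such as hypothesis 2.3 (no change after either regimen), so the mixed ANOVA must stay for those.

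**Readings that go too far.**
- A reader might infer two rival primary models. All the relevant text names the mixed ANOVA; what is missing is a definition of one contingency.
- A reader might infer that the default ignores baseline or is biased. It uses baseline by differencing and is unbiased under randomisation.
- A reader might infer that no covariate is identified. The reference to the variable of interest points to the outcome's own baseline; only the demographics are unnamed.
- A reader might infer that the rule inflates type I error, or that it cannot. A trigger fixed in advance is conservative. The 6–8% is a bound on what the open wording permits, not evidence of how it would be used.

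**Conclusion.** The point holds as a weakness of specification with a near-free improvement. The planned default is not invalid. A trigger based on chance imbalance either loses power (fixed) or leaves the error rate unprotected (open).

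The variance gain from always adjusting is moderate at r = 0.25–0.40 (ratio 1.57–1.40), about 1.2 in the unequal-correlation case and small at 0.84 (1.07). At 0.84 it is nil if the follow-up SD is 1.1–1.2 times baseline. These figures assume bivariate normal distances, 30 per arm and the stated k; the 1.8% bound also assumes a common slope.

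The low absolute power in the table comes from the 30 m difference and the 127 m SD, which is a separate matter. Adjustment does not cure it. From n = 2 × (1.96 + 0.84)² × SD² × (1 − r²)/30², even r = 0.84 needs about 83 per arm for 80% power with ANCOVA, against 91 with the change score.

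**What to change.** Make the change by an amendment dated before any further between-arm look. Timing matters because Sample Size refers to completion rates to date, so the trial is under way. The Data and Safety Monitoring Plan says blinding ends at randomisation and that results are examined on an interim basis.

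- **Analysis:** delete the baseline-difference trigger. Name as primary the ANCOVA of post-regimen 6MWT distance on arm with baseline 6MWT distance as covariate, whatever the baseline comparison shows. Include no demographic covariate unless named in advance.
- **Secondary outcomes, Aims 1–3:** use the same model for between-arm comparisons, each with its own baseline.
- **Mixed ANOVA:** keep it as supportive and for the planned within-group comparisons.
- **Sample Size:** align the primary-test wording and add a power statement for the ANCOVA, so that the new primary model has its own justification. State that adjustment does not by itself bring power to 80%.
- **SD review at 45 completers:** also report the ANCOVA residual SD, so that any change of size matches the primary model.

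The cost is an amendment and a short power calculation. No new data or visits are needed. The analysis population, which the Analysis section does not name, is not settled by this change.

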## Informational Gaps

Outcomes of our preliminary study suggest the value of aerobic training for increasing cardiorespiratory capacity, diminishing fatigue severity, and improving the capacity for performing physical activities in patients with ILD. Increased cardiorespiratory function appears to mediate improvements in PWC, fatigue severity, and physical activity. However the cardiorespiratory adaptation results are somewhat atypical. In many conditions, peak  $\text{VO}_2$  is 15-20% higher after training. This occurs as a result of increases in both central circulatory  $\text{O}_2$  delivery and peripheral  $\text{O}_2$  extraction. In our study of patients with ILD, peak  $\text{VO}_2$  increased only by 4.6% after AET despite a 16.3% increase in peak a- $\text{vO}_2$ . An increase in peak  $\text{Qt}$  was not observed. Resting right ventricular function was within normal ranges,  $\text{Qt}$  increased during exercise, and patients did not become symptomatic of congestive heart failure. Therefore the mechanisms limiting the improvement in peak  $\text{VO}_2$  were likely impaired pulmonary gas exchange and restricted lung function, which are hallmarks of the ILD clinical course.

The mechanistic link to improvement provides relatively strong evidence for a substantial benefit of AET. However, some of the measurements, such as those made at volitional exhaustion, 6MWT distance and questionnaire responses could have been to some degree influenced by motivational factors and familiarity with the testing procedures. Therefore, a RCT is needed before the mechanistic and clinical effects of AET can be determined with confidence. We are proposing a small, phase 2 RCT to establish the safety and efficacy of AET in patients with ILD.

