After completion of the AET+ or control regimens, subjects will undergo the follow up research test battery. The follow up battery consists of echocardiogram, pulmonary function test, arterial occlusion muscle oxygenation test, 6MWT, tCPET, and questionnaires identical to those included in the battery at baseline. Subjects in the control group will subsequently participate in a 10-week AET regimen identical to AET+ except without the educational lectures, since participation in the lectures was completed as the control condition. A second identical, follow up test battery will be completed by this group after the crossover AET regimen is completed. After completion of their AET+, subjects will be contacted monthly with regard to continued exercise habits, the frequency, length, and severity of hospitalizations, or acceptance to a lung transplant waiting list. Mortality will also be assessed at this time.

**Specific Aim 1:** "Determination of the Influence of AET+ on PWC in Patients with ILD".

The main outcome variable for this project is 6MWT distance, which is the most frequently used measure of physical performance for evaluating patients with ILD and other advanced lung diseases. A minimal clinically important difference (MCID) for 6MWT distance has been determined to be approximately 30 meters in ILD. Additional measures of PWC used in this study are peak WR on the tCPET, and performance and perceived fatigability as measured by a modification of the method used by Schnelle and coworkers in an older cohort. We will measure all 4 of these variables at baseline and after the AET+ and control regimens, as well as after the crossover regimen. We hypothesize that:

- 1.1. An increase in 6MWT distance of at least 30 meters longer than control will be observed after AET+.
- 1.2. A significant increase in peak WR will be observed after AET+ compared to control.
- 1.3. A significant decrease in performance fatigability will be observed after AET+ compared to control.
- 1.4. A significant decrease in perceived fatigability will be observed after AET+ compared to control.

- 1.5 In the Sub-study on Crossover we hypothesize that AET will result in improvements over baseline in all of the variables of interest including 6MWT, peak WR, and performance and perceived fatigability that are similar to AET+.

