### **Subject compensation:**

Subjects will be compensated \$300 for each completed testing session at the NIH. For those in the concurrent exercise and education group of the randomized trial, this will amount to \$600 because participants will come to the NIH for initial testing and again for retesting at the end of the study. For those in the education only group the amount of compensation will be \$900 because participants will come to the NIH for initial testing, then again for a second testing after the

completion of 10 weeks of education, and again for a third time after 10 completed weeks of exercise.

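### The crossover analysis names no contrast that isolates the AET period, and measuring improvement from baseline mixes control-period change into the AET effect

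*Combined protocol and SAP*

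**What the plan says.** The Analysis section sets the crossover question: "we will determine if AET+ induces significant improvements in the variables of interest in the CON group". The test is a repeated-measures ANOVA "among baseline, 10-week post control, and 2-week post crossover AET data points". No contrast, direction or follow-up comparison is named; the section adds only a 5% significance level.

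The reference point comes from the hypotheses under Specific Aims 1 to 3. Hypothesis 1.5 reads "In the Sub-study on Crossover we hypothesize that AET will result in improvements over baseline in all of the variables of interest", and 2.4 and 3.5 follow the same pattern. All three also expect the result to resemble that of AET+. The Analysis section gives no comparison for that claim, because the crossover ANOVA uses the CON group alone.

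On timing, Study Design and Methods says: "A second identical, follow up test battery will be completed by this group after the crossover AET regimen is completed". Subject compensation places the last test visit "again for a third time after 10 completed weeks of exercise", and the study coordinator's recruitment script says the same in substance. None of these gives a test window. A two-week figure appears only in the Analysis section.

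The protocol also names both ways in which results can move without AET. Informational Gaps says that effort-dependent measures, 6MWT distance and questionnaire answers "could have been to some degree influenced by motivational factors and familiarity with the testing procedures". Sample Size expects that CON patients may decline as ILD progresses.

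**The concern.** CON patients are tested at baseline, after 10 weeks of education, and after crossover AET. Only the last interval contains AET. A change measured from baseline also contains the education period and the effect of an earlier repeat test.

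The two sources of control-period change act in opposite directions. A familiarity gain is added to the apparent AET benefit. Decline is subtracted from it and can hide a real benefit. The omnibus ANOVA does not separate the intervals either: any difference among the three means can make it significant, whichever interval produced it.

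The claim of similarity to AET+ has a related problem. Measured from baseline, the crossover change spans about 20 weeks and ends at a third test, whereas the AET+ change spans 10 weeks and ends at a second test. These are different quantities.

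**Working it through.** **The plan's own figure.** The plan states no power for the crossover analysis. The nearest figures are for the main trial in Sample Size: effect size f = 0.25 and r = 0.40 need 33 per group for power 0.95, and 20 per group gives 0.803. With λ = f² × N × 2/(1 − r) and 1 and N − 2 degrees of freedom:

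- N = 66: λ = 0.0625 × 66 × 2/0.60 = 13.75, power 0.955
- N = 40: λ = 0.0625 × 40 × 2/0.60 = 8.33, power 0.803

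Both reproduce. This checks the method at f = 0.25 and r = 0.40. It does not show that f = 0.25 follows from SD 127 m and a 30 m gain.

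**Inputs for the crossover.**

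- From Sample Size: n = 30 CON completers; SD 127 m; planning correlations 0.25 to 0.40; correlation 0.840 in the preliminary study, with a weaker value expected in CON.
- From Specific Aim 1: MCID about 30 m.
- Assumed: the same SD and correlation across all three tests (compound symmetry), and control-period shifts of 10, 20 or 30 m.

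**Formulas.** For the ANOVA, λ = n × Σ(mean at each time − overall mean)² / [SD² × (1 − r)], with 2 and 58 degrees of freedom. For a paired contrast, the SD of change is 127 × √(2(1 − r)), which gives 155.5, 139.1 and 71.8 m at r = 0.25, 0.40 and 0.84.

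**Case 1: familiarity gain, AET effect zero.** With shifts from baseline of 0, 30 and 30 m, the sum of squares is 400 + 100 + 100 = 600, and 30 × 600 = 18,000. Since SD² = 16,129, λ = 18,000/(16,129 × 0.60) = 1.86 at r = 0.40, and 18,000/(16,129 × 0.16) = 6.97 at r = 0.84. Percentage of trials significant for gains of 10/20/30 m:

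| r | Three-point ANOVA | Post-AET minus baseline | Post-AET minus post-control |
|---|---|---|---|
| 0.25 | 6/10/17 | 6/11/18 | 5 |
| 0.40 | 6.5/11/20 | 7/12/21 | 5 |
| 0.84 | 11/32/63 | 11/31/60 | 5 |

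In 20,000 simulated trials per setting, the 30 m gain gave 19.9%, 20.5% and 4.7% at r = 0.40, and 62.8%, 60.1% and 4.9% at r = 0.84.

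**Case 2: 30 m decline, then a true 30 m AET gain.** The mean change from baseline is 0 m, so that contrast rejects in 5%. Post-AET minus post-control averages +30 m and rejects in 21% (r = 0.40) or 60% (r = 0.84).

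**Case 3: lasting 30 m decline, AET effect zero.** The ANOVA is again significant in 20% (r = 0.40) or 63% (r = 0.84), but the change from baseline is −30 m.

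**Similarity to AET+.** For the difference between two independent mean changes with 30 per group, the 95% half-width is 2.00 × SD of change × √(2/30):

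- r = 0.84: 2.00 × 71.8 × 0.258 = 37 m
- r = 0.40: 2.00 × 139.1 × 0.258 = 72 m

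Both exceed the 30 m MCID.

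**The case against.** The strongest defence is that the Analysis section does include the post-control test. A three-level ANOVA is commonly followed by pairwise comparisons, so the right contrast is available in the planned model. That is true, and it makes the correction easy. But no such comparison is named, and the only stated reference point, in the hypotheses, is baseline.

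The shift sizes are assumptions. Sample Size simulates no change in CON, and Background reports no significant CON improvement over baseline in the team's randomized study in pulmonary arterial hypertension. This counts against a large familiarity gain. It does not establish a zero gain in ILD, and the direction of the problem does not depend on its size.

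Four stronger readings might be inferred, and the documents do not support them:

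- *Decline is credited to AET.* It is not. Decline can make the omnibus test significant, but it lowers the change from baseline.
- *The two-week label contradicts the schedule.* Read as a two-week AET course, in parallel with the post-control label, it conflicts with the other sections. Read as two weeks after AET ends, it fits them, because they give no window. It is unreconciled, not proven wrong.
- *The r = 0.84 results are the expected size.* That correlation comes from a single-arm preliminary study. The plan uses 0.25 to 0.40 and expects a weaker correlation in CON, where the error rates are much lower.
- *Familiarity affects every outcome equally.* Specific Aim 2 says that AT-time and muscle oxygenation are not influenced by subjective factors. For hypothesis 2.4 the case rests mainly on decline and the mixed interval.

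**Conclusion.** The concern holds in this form: the crossover question is about the AET period, but the plan neither names a contrast for that period nor uses the post-control value as its reference. Followed as written, it mixes control-period change into the AET effect.

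The size depends on assumptions that the documents cannot settle. For a 30 m familiarity gain and no AET effect, false-positive rates run from about 17% at the low end of the planning correlations to about 60% at the preliminary-study correlation, against 5% for the AET-period contrast. All figures assume 30 patients, SD 127 m and compound symmetry.

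The AET-period contrast is less biased but not clean. It has no concurrent control, so any familiarity or progression after the post-control test remains in it. Its power for a true 30 m gain is also low at the planning correlations: 18% at r = 0.25 and 21% at r = 0.40.

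This is a secondary analysis. The primary claim rests on the randomized comparison of AET+ with CON, which this point does not touch.

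**What to change.** 1. In the Analysis section, name post-crossover AET minus 10-week post-control, with a 95% confidence interval, as the crossover test for each outcome. Report baseline to post-control separately.
2. In hypotheses 1.5, 2.4 and 3.5, replace baseline with the post-control value as the reference.
3. For similarity to AET+, report the difference between the AET+ change and the crossover AET-period change with its 95% confidence interval. Do not infer similarity from p > 0.05.
4. State that the crossover contrast has no concurrent control.
5. Reconcile the two-week label with Study Design and Methods, the recruitment script and Subject compensation, and state the intended test window.

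Items 1 to 4 cost only wording and use the same data and model. Item 5 is also wording if the label is a drafting slip; if it reflects a real interval, the schedule sections need to say so.
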